## **10.4 Statistical Analyses**

Below is a description of planned statistical analyses. Further details are presented in the Statistical Analysis Plan (SAP).

### **10.4.1 General Considerations**

Data will be presented using appropriate summary statistics and patient data listings. In general, missing values will not be replaced unless otherwise stated. Baseline will be considered the latest assessment before first dose of study treatment.

A flow diagram of participant progress will be provided, including the number assessed for eligibility and reasons for exclusion, number enrolled, and participants with early withdrawal from the study, together with the primary reasons for discontinuations. Any recorded protocol deviations will be listed.

### **10.4.2 Primary Endpoint**

In Part 1, the primary endpoint is the proportion of patients tolerating RESP301 at each dose level in (according to pre-defined criteria).

In Part 2, the primary endpoint is the feasibility of self-administering RESP301 treatment with nebuliser [REDACTED]

Term	Percentage
GMOs	~10%
Organic	~75%
Natural	~85%
Artificial	~15%
Organic	~75%
Natural	~85%
Artificial	~15%
Organic	~75%
Natural	~85%
Artificial	~15%

### 10.4.3 Secondary Endpoint(s)

The secondary endpoints, which will be analysed on the full cohort and separately in the sub-cohort of those who test positive for SARS-CoV-2, are safety and tolerability and efficacy of RESP301. The endpoints are further defined below.

## 2) Efficacy of RESP301 [REDACTED]

- [REDACTED]
- [REDACTED]
- [REDACTED]
- [REDACTED]
- [REDACTED]
- [REDACTED]
- [REDACTED]
- [REDACTED]

### 10.4.4 Other Analyses

Other analyses may be added to the SAP as applicable.

### 10.5 Interim Analyses

No formal statistical interim analysis is planned.

### 10.6 Data Monitoring Committee (DMC)

An IDMC will be responsible for closely reviewing the safety data and for providing their recommendations on continuation of the study. The detailed procedures and schedule of the meetings will be described in the DMC Charter.

## 11 Regulatory, Ethical, and Study Oversight Considerations

### 11.1 Regulatory and Ethical Considerations

- This study will be conducted in accordance with the protocol and with:
  - Consensus ethical principles derived from international guidelines including the Declaration of Helsinki and Council for International Organizations of Medical Sciences (CIOMS) International Ethical Guidelines.

- Applicable International Council for Harmonisation (ICH) Good Clinical Practice (GCP) Guidelines.
- Applicable laws and regulations.
- The protocol, protocol amendments, ICF, Investigator Brochure, and other relevant documents (e.g., advertisements) must be submitted to an IRB/IEC by the Investigator and reviewed and approved by the IRB/IEC before the study is initiated.
- Any amendments to the protocol will require IEC/IRB approval before implementation of changes made to the study design, except for changes necessary to eliminate an immediate hazard to study participants.
- The Investigator will be responsible for the following:
  - Providing written summaries of the status of the study to the IRB/IEC annually or more frequently in accordance with the requirements, policies, and procedures established by the IRB/EC.
  - Notifying the IRB/IEC of SAE or other significant safety findings as required by IRB/IEC procedures.
  - Overall conduct of the study at the site and adherence to requirements of 21 Code of Federal Regulations (CFR), ICH GCP guidelines, the IRB/IEC, European regulation 536/2014 for clinical studies (if applicable), and all other applicable local regulations.

## 11.2 Informed Consent Process

The Investigator or his/her representative will explain the nature of the study to the participant and answer all questions regarding the study.

Participants must be informed that their participation is voluntary. Participants will be required to sign a statement of informed consent that meets the local regulations, ICH guidelines, and the IRB/IEC or study centre.

The medical record must include a statement that written informed consent was obtained before the participant was enrolled in the study and the date the written consent was obtained. The authorised person obtaining the informed consent must also sign the ICF.

A copy of the ICF(s) must be provided to the participant.

If a protocol amendment is required, the ICF may need to be revised to reflect the changes to the protocol. If the ICF is revised, it must be reviewed and approved by the appropriate IEC/IRB and signed by all participants subsequently enrolled in the study as well as those

currently enrolled in the study if they are affected by the revisions. A measured approach should be taken to determine which participants need to be reconsented.

### **11.3 Data Protection**

Participants will be assigned a unique identifier by the Sponsor. Any participant records or datasets that are transferred to the Sponsor will contain the identifier only; participant names or any information which would make the participant identifiable will not be transferred.

The participant must be informed that his/her personal study-related data will be used by the Sponsor in accordance with local data protection law. The level of disclosure must also be explained to the participant who will be required to give consent for their data to be used as described in the informed consent.

The participant must be informed that his/her medical records may be examined by Clinical Quality Assurance auditors or other authorised personnel appointed by the Sponsor, by appropriate IRB/IEC members, and by inspectors from regulatory authorities.

### **11.4 Committees Structure**

An IDMC will be responsible for closely reviewing the safety data and for providing their recommendations on continuation of the study (see Sections 10.5 and 10.6).

### **11.5 Data Quality Assurance**

- All participant data relating to the study will be recorded on printed or electronic CRF unless transmitted to the Sponsor or designee electronically (e.g., laboratory data). The Investigator is responsible for verifying that data entries are accurate and correct by physically or electronically signing the CRF.
- The Investigator must maintain accurate documentation (source data) that supports the information entered in the CRF.
- The Investigator must permit study-related monitoring, audits, IRB/IEC review, and regulatory agency inspections and provide direct access to source data documents.
- Monitoring details describing strategies (e.g., risk-based initiatives in operations and quality such as Risk Management and Mitigation Strategies and Analytical Risk-Based Monitoring), methods, responsibilities and requirements, including handling of noncompliance issues and monitoring techniques (central, remote, or on-site monitoring) are provided in the Monitoring Plan.
- The Sponsor or designee is responsible for the data management of this study including quality checking of the data.

- The Sponsor assumes accountability for actions delegated to other individuals (e.g., Contract Research Organisations [CROs]).
- Study monitors will perform ongoing source data verification to confirm that data entered into the CRF by authorised site personnel are accurate, complete, and verifiable from source documents; that the safety and rights of participants are being protected; and that the study is being conducted in accordance with the currently approved protocol and any other study agreements, ICH GCP, and all applicable regulatory requirements.
- Records and documents, including signed ICF, pertaining to the conduct of this study must be retained by the Investigator for at least 2 years after the last approval of a marketing application or 15 years from completion of the study, whichever is longer according to the relevant local laws and/or regulations. No records may be destroyed during the retention period without the written approval of the Sponsor. No records may be transferred to another location or party without written notification to the Sponsor.
- All data generated by the site personnel will be captured electronically at each study center using eCRFs. Once the eCRF clinical data have been submitted to the eCRF, corrections to the data fields will be captured in an audit trail. The reason for change, the name of the person who performed the change, together with the time and date will be logged to provide an audit trail.
- If additional corrections are needed, the responsible monitor or data manager will raise a query in the electronic data capture (EDC) application. The appropriate staff at the study site will answer queries sent to the Investigator. The name of the staff member responding to the query, and time and date stamp will be captured to provide an audit trail.
- The specific procedures to be used for data entry and query resolution using the EDC system/eCRF will be provided to study sites in a training manual. In addition, site personnel will receive training on the EDC system/eCRF.

## 11.6 Source Documents

Source documents provide evidence for the existence of the participant and substantiate the integrity of the data collected. Source documents are filed at the Investigator's site.

Data reported on the CRF or entered in the eCRF that are transcribed from source documents must be consistent with the source documents or the discrepancies must be explained. The Investigator may need to request previous medical records or transfer records, depending on the study. Also, current medical records must be available.

## 11.7 Study and Site Start and Closure

The study start date is the date on which the clinical study will be open for recruitment of participants. The first act of recruitment is the first participant signing the informed consent form and will be the study start date.

The Sponsor designee reserves the right to close the study site or terminate the study at any time for any reason at the sole discretion of the Sponsor. Study sites will be closed upon study completion. A study site is considered closed when all required documents and study supplies have been collected and a study site closure (on site visit or remote closure) has been performed.

The Investigator may initiate study site closure at any time, provided there is reasonable cause and sufficient notice is given in advance of the intended termination.

Reasons for the early closure of a study site by the Sponsor or Investigator may include but are not limited to:

- Failure of the Investigator to comply with the protocol, the requirements of the IRB/IEC or local health authorities, the Sponsor's procedures, or GCP guidelines
- Inadequate recruitment of participants by the Investigator
- Discontinuation of further study intervention development

If the study is prematurely terminated or suspended, the Sponsor shall promptly inform the Investigators, the IECs/IRBs, the regulatory authorities, and any CRO(s) used in the study of the reason for termination or suspension, as specified by the applicable regulatory requirements. The Investigator shall promptly inform the participant and should assure appropriate participant therapy and/or follow-up.

## 11.8 Publication Policy

- The results of this study may be published or presented at scientific meetings. If this is foreseen, the Investigator agrees to submit all manuscripts or abstracts to the Sponsor at least one month before submission. This allows the Sponsor to protect proprietary information and to provide comments.
- The Sponsor will comply with the requirements for publication of study results. In accordance with standard editorial and ethical practice, the Sponsor will generally support publication of multicentre studies only in their entirety and not as individual site data. In this case, a coordinating Investigator will be designated by mutual agreement.
- Authorship will be determined by mutual agreement and in line with International Committee of Medical Journal Editors authorship requirements.

## **11.9 Protocol Approval and Amendment**

Before the start of the study, the study protocol and/or other relevant documents will be approved by the IEC/IRB/Competent Authorities, in accordance with local legal requirements. The Sponsor must ensure that all ethical and legal requirements have been met before the first participant is enrolled in the study.

This protocol is to be followed exactly. To alter the protocol, amendments must be written, receive approval from the appropriate personnel, and receive IRB/IEC/Competent Authority approval prior to implementation (if appropriate).

Administrative changes (not affecting the participant benefit/risk ratio) may be made without the need for a formal amendment. All amendments will be distributed to all protocol recipients, with appropriate instructions.

## **11.10 Liability and Insurance**

The study Sponsor holds a Clinical Trials Insurance for legal liabilities arising in relation to this trial. NHS bodies are legally liable for the negligent acts and omissions of their employees. If a patient is harmed whilst taking part in a clinical study as a result of negligence on the part of a member of the study team this liability cover would apply.

## **11.11 Access to Source Data**

Access to source data is described in the Clinical Trial Agreement for each site.

## Appendix 1: Adverse Events: Definitions and Procedures for Recording, Evaluating, Follow-up, and Reporting

### Definition of AE

AE Definition

• An AE is any untoward medical occurrence in a patient or clinical study participant, temporally associated with the use of a study intervention, whether or not considered related to the study intervention.

• NOTE: An AE can therefore be any unfavorable and unintended sign (including an abnormal laboratory finding), symptom, or disease (new or exacerbated) temporally associated with the use of a study intervention.

Events Meeting the AE Definition

• Any abnormal laboratory test results (hematology, clinical chemistry, or urinalysis) or other safety assessments (e.g., ECG, radiological scans, vital signs measurements), including those that worsen from baseline, considered clinically significant in the medical and scientific judgment of the Investigator (e.g., not related to progression of underlying disease).

• Exacerbation of a chronic or intermittent pre-existing condition including either an increase in frequency and/or intensity of the condition.

• New conditions detected or diagnosed after study intervention administration even though it may have been present before the start of the study.

• Signs, symptoms, or the clinical sequelae of a suspected drug-drug interaction.

• Signs, symptoms, or the clinical sequelae of a suspected overdose of either study intervention or a concomitant medication. Overdose per se will not be reported as an AE/SAE unless it is an intentional overdose taken with possible suicidal/self-harming intent. Such overdoses should be reported regardless of sequelae.

• "Lack of efficacy" or "failure of expected pharmacological action" per se will not be reported as an AE or SAE. Such instances will be captured in the efficacy assessments. However, the signs, symptoms, and/or clinical sequelae resulting from lack of efficacy will be reported as AE or SAE if they fulfill the definition of an AE or SAE.

Events NOT Meeting the AE Definition


• Any clinically significant abnormal laboratory findings or other abnormal safety assessments which are associated with the underlying disease, unless judged by the Investigator to be more severe than expected for the participant's condition.

• The disease/disorder being studied or expected progression, signs, or symptoms of the disease/disorder being studied, unless more severe than expected for the participant's

condition.

- Medical or surgical procedure (e.g., endoscopy, appendectomy): the condition that leads to the procedure is the AE.
- Situations in which an untoward medical occurrence did not occur (social and/or convenience admission to a hospital).
- Anticipated day-to-day fluctuations of pre-existing disease(s) or condition(s) present or detected at the start of the study that do not worsen.

## Definition of SAE

If an event is not an AE per definition above, then it cannot be an SAE even if serious conditions are met (e.g., hospitalisation for signs/symptoms of the disease under study, death due to progression of disease).

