	
To be evaluated on the full cohort, and separately in the sub-cohort of those who test positive for SARS-CoV-2:
 

• Safety and tolerability of RESP301 in terms of:

○ % of participants able to tolerate the test dose in Parts 1(a), 1 (b) and 2

○ Total counts and cumulative incidence of:

▪ Adverse Events (AEs)

▪ Serious Adverse Events (SAEs)

▪ Suspected Unexpected Serious Adverse Reactions (SUSARs)

▪ Severe AEs

▪ Treatment-related AEs/SAEs

• Feasibility in terms of percentage of patients who, having experienced and correctly reported an exacerbation, receive the treatment within 48 hours of reporting their exacerbation

• Efficacy of RESP301 in terms of:

○ % of participants recovered by Day 7 and Day 14 post starting treatment

○ time to recovery (days until patient feels all their symptoms are back to their usual baseline (all VAS = 0))

○ preventing exacerbation-related hospitalisation and/or death

○ change in CCQ score

Duration of participation in the study	The overall study duration for each participant will be at most approximately 60 weeks, including one or more visits at a study centre in Parts 1/2, monthly follow-up calls, and, for those who experience an exacerbation, one week of treatment and additional monitoring calls at the beginning, during and following the treatment period.
Study population	Participants will be adult patients with spirometry-confirmed COPD or computerised tomography (CT) proven bronchiectasis, recruited from secondary and primary care sites in the UK.
Sample size	
Part 1(a):
 
We aim to recruit up to 48 participants. All participants who complete Part 1a, will also be eligible to enter Part 2 of the trial.
 
Part 1(b):
 
We aim to recruit 8 participants who are not experiencing an exacerbation. These participants will receive a short acting

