## **9.6 Disease-Related Events and/or Disease-Related Outcomes Not Qualifying as AEs or SAEs (Not Applicable)**

## **9.7 Adverse Events of Special Interest (Not Applicable)**

No AEs of special interest are defined for this study.

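### Appendix 1 has no rule for classifying an exacerbation, or its worsening, after RESP301, and a disease-related hospitalisation or death could be missing from both the safety and the efficacy tables

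*Protocol*

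**What the plan says.** Four places in the protocol bear on how an exacerbation is classified.

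- Appendix 1, events meeting the AE definition: "Exacerbation of a chronic or intermittent pre-existing condition including either an increase in frequency and/or intensity of the condition".
- Appendix 1, events not meeting the AE definition: "The disease/disorder being studied or expected progression, signs, or symptoms of the disease/disorder being studied, unless more severe than expected for the" participant's condition. This list does not use the word exacerbation.
- Appendix 1, Definition of SAE, opening sentence: if an event does not meet the AE definition, "then it cannot be an SAE even if serious conditions are met (e.g., hospitalisation for signs/symptoms of the disease under study"; the second example is death from progression of the disease). The examples do not repeat the severity exception. The definition that follows covers any untoward medical occurrence with a serious outcome.
- Section 9.6: "Disease-Related Events and/or Disease-Related Outcomes Not Qualifying as AEs or SAEs (Not Applicable"). There is no text under the heading.

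The synopsis lists "preventing exacerbation-related hospitalisation and/or death" among the secondary efficacy endpoints. Protocol 10.4.3 summarises deaths and hospitalisations only where they are due to an AE. SAP 3.1 and the SAP lists of efficacy and safety tables (15.2 and 15.3) name neither hospitalisation nor death.

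**The concern.** Exacerbation is the condition being treated, so the line between disease and adverse event matters more here than in most trials. The symptoms that trigger treatment include increased cough or wheeze. The harms watched for in Part 1 are troublesome cough, chest pain or tightness, bronchospasm and dyspnoea. During a treated exacerbation at home, airway worsening caused by the inhaled product can look like the disease.

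The study is single-arm and open-label. No comparator rate would expose misclassification, and deciding what is more severe than expected is a case-by-case judgement by an investigator who knows the treatment. Safety and tolerability is a secondary objective. An event recorded as disease leaves the AE and SAE counts, so the error runs toward looking safer. The 24-hour SAE notice and the SUSAR rules depend on the same classification.

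**Working it through.** The point rests on comparing texts; the plan gives no figure to reproduce. Take a participant on the home course who is admitted with worsening wheeze and breathlessness, and follow the text.

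**Step 1: is it an AE?**

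| Reading | Basis in Appendix 1 | Result |
|---|---|---|
| A | Exacerbation of a pre-existing condition | AE |
| B | Expected sign or symptom of the disease under study | Not an AE |
| C | As B, but judged more severe than expected | AE |

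Nothing visible says which list prevails, or what severity is expected in a participant who entered treatment because of an exacerbation.

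**Step 2: is it an SAE?** Under A or C, inpatient admission meets a serious criterion and the event is an SAE. Under B the opening sentence of the SAE definition removes it, and the attached example describes this kind of admission. Two investigators could each follow the text and classify the same admission oppositely.

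**Step 3: does section 9.6 settle it?** No. Its heading is where disease-related exemptions would be defined. Marked Not Applicable, it suggests that there are none, yet the Appendix 1 examples supply one.

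**Step 4: where is it counted?** Under B it is outside the AE and SAE tables and outside the 10.4.3 counts of deaths and hospitalisations. Appendix 1 sends lack of efficacy to the efficacy assessments. The efficacy endpoint that would catch the event is in the synopsis but not in SAP 3.1 or the SAP table list. The event can therefore be absent from both sets of tables.

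**Step 5: scale.**

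- Inputs: SAP section 4 expects 30 of 150 participants to exacerbate, 30/150 = 20%, and has the first 50 receive a test dose. SAP 5.11 counts as treatment-emergent an AE that begins after the first administration.
- Assumption: the 20% applies to the 50 test-dosed participants, all of whom enter the dormant period. Then 0.20 × 50 = 10 exacerbations begin after first drug.
- If the first list governs, 10 are treatment-emergent AEs. If the second governs and none is judged more severe than expected, 0 are.
- If all 150 were test-dosed, 0.20 × 150 = 30, and the range is 0 to 30.
- In participants without a test dose, the exacerbation that leads to treatment precedes the first dose and is not treatment-emergent on either reading. Only its later worsening is in doubt.

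The documents give no hospitalisation rate. If, purely as an assumption, 3 of 30 treated participants were admitted for the exacerbation, the SAE count could be anything from 0/30 to 3/30 = 10%. The zero end is the extreme case, in which every admission is judged expected disease.

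**The case against.** A reader might infer that Appendix 1 bars a hospitalised or fatal exacerbation from being an SAE. It does not. The bar is conditional on the event not being an AE, and the severity exception lets an investigator class such an event as an AE and then as an SAE. Another bullet says that the consequences of lack of efficacy are reported if they meet the AE or SAE definition. That helps only in part, because it refers back to the same definitions.

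The two lists can also be reconciled by treating the rule for the disease under study as a carve-out from the general rule on pre-existing conditions. That is a reasonable reading, but the text does not state it, and it leads to reading B.

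A reader might also take section 9.6 as stating that no exemption applies. A bare heading only implies this; it may mean that no separate category of disease-related events was set up.

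Nor do airway symptoms escape capture throughout. In Part 1 they are named as treatment-related AEs, and SAP 3.1 counts them as failure to tolerate the test dose in Parts 1(a), 1(b) and 2. The gap for drug-related airway worsening is therefore mainly in the home treatment period. A death might also surface as a reason for withdrawal in the disposition outputs, but nothing there counts exacerbation-related deaths or admissions.

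Finally, the detailed efficacy list in protocol 10.4.3 and much of section 8.4 are blacked out, so handling there cannot be seen. SAP 3.1 and the SAP table lists are readable, and the endpoint is not in them.

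**Conclusion.** The point stands as a missing classification rule. It is not a prohibition on reporting exacerbations as SAEs. The visible text lets the same post-dose exacerbation, including one ending in hospitalisation or death, be either an SAE or not an AE. Because the SAP omits the synopsis endpoint, an event classed as disease could appear in no safety or efficacy table.

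The direction is toward looking safer. The size depends on investigators' judgement and cannot be fixed from the documents. The ranges in the working assume the SAP's 20% exacerbation rate, and their zero ends assume that no event is judged more severe than expected. The plan should be changed, because the fix is cheap and AE and SAE counts are named secondary endpoints.

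**What to change.** 1. Reconcile protocol section 9.6 with the AE and SAE definitions in Appendix 1 through one explicit reporting rule. For example: respiratory worsening from the start of RESP301 dosing is recorded as an AE and, if it meets one of the listed serious criteria, as an SAE, even when attributed to the disease. Keep the existing exclusions for social or convenience admissions and for elective admissions; a rule making every hospitalisation an SAE would contradict them.
2. State whether the rule runs from the test dose or from the first home dose. The schedule of activities shows no AE review in the dormant-period calls, so starting at the test dose would need one added.
3. Add to SAP 3.1 and the SAP table list a count of all hospitalisations and deaths after dosing, with exacerbation-related ones shown separately, regardless of AE classification. This also restores the synopsis endpoint.

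The cost is a short protocol amendment, one more table row and a few more SAE forms. If the rule starts at the test dose, add an AE question to the monthly calls.
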